## Synopsis

Uncontrolled hypertension is a key factor in the rising epidemic of cardiovascular diseases (CVD), especially in low and middle income countries (LMIC). Nevertheless, research on the main gaps in hypertension care and control and studies evaluating health services interventions to improve hypertension care in LMIC remain scarce. The US Centers for Disease control and Prevention and the Pan American Health Organization recently developed the Standardized Hypertension Treatment and Prevention (SHTP) Project, which was followed by the World Health Organization's initiative "Hearts in the Americas". Both projects provide a practical approach to improve CVD prevention and management using hypertension as the entry point.

In Colombia, 30% of all deaths and 16% of Years of Life Lost can be attributed to CVD. A cross-sectional survey carried out in 2016 in a low-income community in Medellin, aimed to estimate the prevalence of hypertension among the population aged 35 years or older and the magnitude and the determinants of the main gaps in hypertension care and control (utilization of health services, diagnosis, treatment, follow-up) showed a prevalence of hypertension of 43.4%. Among all hypertensive individuals, 36.7% were unaware of their diagnosis. Among the aware hypertensives, 41% had uncontrolled hypertension; 55% of unaware hypertensives had accessed health care in the previous year but health services had failed to diagnose them.

Based on the technical recommendations contained in the SHTP Project, the Technical Package of the "Hearts in the Americas" initiative, on the results of the above-mentioned cross-sectional survey and in consultation with the local partners (Metrosalud and the University of Antioquia) and community leaders, a multi-component intervention for the improvement of hypertension care and control was designed. The components of the intervention integrate activities related to: A) Health services organization, B) Training of clinical staff and C) Patients and community engagement.

The effectiveness of the intervention in reducing the gaps in hypertension care and control will be evaluated in a quasi-experimental, controlled before-after trial, with an intervention arm (a commune of Medellin) where the intervention is deployed and a control arm (another commune of Medellin, with similar socio-economic characteristics) where routine care is implemented. As baseline, the results of the population-based cross-sectional study "Gaps in hypertension care and control in Medellin, Colombia: cross-sectional survey in two Communes", Version 2.0, dated 26-AUG-2018, approved by the UZA Ethics committee on 15/10/2018, will be used. Two years after the start of the intervention, a repeat survey using the same methodology as in the baseline will be carried out in the two communes. The main outcomes (gaps in hypertension care and control) will be assessed with difference in difference measures (endline-baseline changes in the intervention minus endline-baseline changes in the control commune).

The study aims at contributing to the improvement of hypertension care and control in Colombia and may inspire and inform with scientific evidence other initiatives for better chronic care in LMIC, especially in Latin America.

## 1. INTRODUCTION

### 1.1 Background

Non-communicable diseases (NCD) are estimated to account for 63% of global mortality nowadays and it is predicted that they will account for around 70% of global deaths by 2030(1). NCD are especially worrying for developing countries, where their incidence is increasing disproportionately. Four out of five deaths caused by chronic conditions occur in low and middle-income countries (LMIC)(2). NCD are also the first cause of mortality and disability in Latin America and the Caribbean (LAC)(3). Notwithstanding, the majority of health systems provide inadequate chronic diseases management, with health services mainly designed for acute curative care. Chronic care, especially in developing countries, is often reduced to the belated management of acute exacerbations of chronic illnesses in specialized settings and at high costs. Consequently, only about one in ten people with chronic conditions are treated successfully(3) and most out-of-pocket health payments and catastrophic expenditure are related to these conditions(4).

Uncontrolled hypertension is the main modifiable risk factor for cardiovascular diseases (CVD) and the related cause of more than 10 million deaths each year(2). Approximately 65% of deaths due to stroke and 50% of deaths due to ischemic heart disease are attributable to uncontrolled hypertension. Furthermore, almost three quarters of people suffering from hypertension (650 million people) live in developing countries, where disease awareness is very low and access to health care is very limited(2;5). Hence, the risk of dying from hypertension at all ages is more than double in LMIC compared to high income countries (HIC)(6).

CVD are significantly related to premature mortality and disability, hampering economic growth and social development. Current epidemiological data point to CVD striking the working middle-age population in LMIC(7). An estimated 1.6 million people die from CVD every year in LAC (38% of all deaths), half a million of them before 70 years of age(8). High disease prevalence and poor hypertension control are pivotal factors in the rising epidemic of CVD in LMIC(5). Nevertheless, very limited descriptive research in this field has been conducted in LMIC(9). A more in depth assessment of the actual hypertension care and control coverage in LMIC is necessary. Such health coverage evaluation, as stated by Tanahashi(10), requires an assessment at population level.

The recent Prospective Urban Rural Epidemiology (PURE) study in 3 HIC and 14 LMIC(11), found an average age-standardized prevalence of hypertension of 27.7% in adults aged 35 to 70 years. Only 46.5% of participants were aware of their condition; among those aware, 87.5% were receiving

pharmacological treatment but only a minority of treated patients (32.5%) were controlled. The PURE study provided relevant information regarding international rates of hypertension awareness, treatment and control. However, it did not explore the health coverage gaps throughout the hypertension continuum of care nor their determinants. The hypertension continuum of care is a dynamic and interrelated process, from detection to control, that includes access to health services, diagnosis, treatment and follow-up. We define gaps in hypertension care and control as the differences between the actual state of the main components of the continuum of care in a given context and time, compared to the optimal state of each of these components, according to the available evidence and/or the international standards.

There are studies trying to identify patient and health care provider barriers to hypertension care(9), most of them carried-out in HIC and gathering information at health facility level, without including any population assessment. As a result, there is scarce evidence on the main determinants of the gaps in hypertension care and control, especially regarding access to health services and hypertension diagnosis in LMIC.

The Chronic Care Model(12) and its expanded version(3) are the main international references to guide interventions for improving chronic disease management. Nevertheless, studies evaluating health services interventions to improve hypertension care in LMIC are still much more scanty than purely descriptive research. Notwithstanding, in order to provide a practical approach to improve CVD prevention and management using hypertension as the entry point, the US Centers for Disease control and Prevention and the Pan American Health Organization developed the Standardized Hypertension Treatment and Prevention (SHTP) Project(2). The SHTP Project identified six key elements of standardized hypertension management to be addressed to strengthen health systems at primary care level and to improve hypertension control, using evidence-based interventions(2): guideline-based standardized treatment protocols; medications; registries for cohort monitoring and evaluation; patient empowerment; team-based care system; community engagement. This approach was reinforced by the World Health Organization global initiative “Global Hearts” through the Technical Package for Cardiovascular Disease Management in Primary Health Care(13).

In summary, research to document the main gaps and barriers hampering hypertension care and control at population level in LMIC is needed. Furthermore, operational research aimed to improve hypertension care and control and to reduce CVD morbidity and mortality is urgently required throughout the Latin America region.

## 1.2 Rationale

In Colombia, the death rate from CVD in 2014 was 146.9 per 100.000 population. In this country, 30% of all deaths and 16.3% of Years of Life Lost can be attributed to CVD (14). The Colombian health system is divided in two different regimes, according to individuals' payment capacity. People able to contribute to the social security system and their beneficiaries are affiliated to the Contributory Regime, which is compulsory for formal employees and pensioners. The Subsidized Regime is financed by the State and covers the poor un-employed or informal-employed population. In Colombia, in the context of a market-oriented health system, cost-containment mechanisms imposed by health insurance companies often hamper timely access to health care, especially for those chronically ill, generating harmful consequences to people's lives (15).

In 2016 we carried out a cross-sectional survey in a low-income urban community in Medellin, aimed to estimate the prevalence of hypertension among the population aged 35 years or older and the magnitude and the determinants of the main gaps in hypertension care and control (Table 1).

**Table 1.** Main Gaps in hypertension care and control – definitions.

Gap	Numerator	Denominator	Remarks
Diagnosis	Number of unaware hypertensive individuals	The total surveyed population	Also calculated for hypertensives (nr. unaware /total hypertensives)
Pharmacological treatment	Number of aware hypertensive individuals who received prescription of antihypertensive medications but do not take any antihypertensive drug	Aware hypertensive individuals who received prescription of antihypertensive medications	
Follow-up	Number of aware hypertensive individuals who did not receive a follow-up consultation in the last year	Number of aware hypertensive individuals	

Control	Number of aware hypertensives with uncontrolled hypertension + Number of unaware hypertensives	The total hypertensive population (aware + unaware)	Also calculated in subgroup aware hypertensives
---------	--	---	---

The study showed a prevalence of hypertension of 43.4%. Among the total hypertensive individuals, 36.7% were unaware of their diagnosis. Of the aware hypertensives, 93% had been prescribed pharmacological treatment, but 7% of those who had been prescribed treatment were not taking any medication and only 65% of those taking treatment referred treatment compliance. Moreover, 15% of the aware hypertensives did not have any follow-up consultation during the previous year. Among the aware hypertensives, 41% had uncontrolled hypertension. Nineteen percent of aware hypertensives and 45% of unaware hypertensives did not have contact with formal health services in the last year, mainly because they did not feel the need. On the other hand, 55% of unaware hypertensives accessed to health care in the previous year but health services failed to diagnose them.

Studies specifically aimed at reducing the gaps and barriers to hypertension care and control at population level in the country are needed.

The results of the baseline study, the possible determinants of the identified gaps and potential solutions were discussed in a workshop held in Medellin-city, with the participation of ITM staff, the University of Antioquia and Metrosalud. A summary of the identified potential determinants of the main gaps, mainly related to disease detection and quality of care, is presented in Table 2.

**Table 2. Potential determinants at health provider, population and health system level of the main health coverage gaps for hypertension care and control in the Santa Cruz Commune**

Hypertension Coverage Gap / Source of barriers	Health Provision	Population	Health Services
Diagnosis Gap	
 
- No measurement of blood pressure during health care contacts
 
- High blood pressure is detected but confirmation of diagnosis fails due to lack of continuity of care
 
	
 
- Low risk perception of hypertension
 
- Mild or no symptoms determine health seeking
 
	
 
- Passive and fragmented health services
 
- Limited opening hours of services for hypertension detection
 

Quality of care (treatment and follow-up)	
 
- No pharmacological advise/consultation
 
- Limited communication skills of health staff and poor doctor-patient relationship
 
- Interrupted delivery of essential anti-hypertensive drugs
 
	
 
- Low awareness of the importance of non-pharmacological measures
 
- Low educational level
 
	
 
- Scarcity of essential anti-hypertensive drugs
 
- Administrative barriers imposed to patients and health providers
 

Based on the technical recommendations contained in the SHTP Project and the “Hearts in the Americas” initiative, on the results of the baseline study and in consultation with the local partners (Metrosalud - the main public health care provider of Medellin city - and the University of Antioquia) and community leaders, we designed, during repeated workshops, a multi-component intervention for the improvement of hypertension care and control in individuals aged 35 years or older in Medellin.

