## 2. STUDY OBJECTIVES

### **Main objective:**

To implement and evaluate the effectiveness of a multi-component intervention with evidence-based activities, to reduce the gaps in hypertension care and control at population level

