#### 4.1.4 Definitions

Hypertensive individual (operational definition for survey): self-report of previously diagnosed hypertension or without previous diagnosis but presenting an average blood pressure (BP) measurement higher than 140/90 mmHg(11;16).

Presumptive hypertensive individual: no self-report of previously diagnosed hypertension but presenting an average BP measurement higher than 140/90 mmHg.

Controlled hypertensive individual: self-report of previously diagnosed hypertension and an average BP less than 140/90 mm Hg for patients between 35 and 59 years old or diabetics and 150/90 mm Hg for patients aged 60 years or older (17).

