## C. Patients and community engagement

- C.1. Patient empowerment: sessions where "expert hypertensive patients" will provide support and peer-education to other patients in need, such as those newly diagnosed or non-adherent to treatment or with uncontrolled hypertension, under the supervision of a social worker.
- C.2. Community engagement: A Community Hypertension Outreach Group (CHOG) will be set up, composed by three voluntary community health workers who will be trained and certified. The CHOG will be created in partnership with the patients' association, which is a very dynamic organization already present in the Commune and interested in engaging in the project. The CHOG will conduct screening activities with measurements of BP in selected public areas of the commune on a weekly rotation basis, for all adults without BP readings in the previous year and referral of those with a positive screening to the nearest health facility for diagnosis confirmation. The CHOG will provide health education with emphasis on healthy lifestyles (tobacco cessation, physical activity and healthy diet). It will contribute to increase community awareness on the importance of hypertension control and on cardiovascular risk detection and prevention. Existing local communication channels such as the community radio and the local newspaper will also be used.

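### New diagnoses in people whose survey blood pressure would have been normal anyway enlarge the control gap's denominator but not its numerator, so case-finding added in one commune can lower the gap without a matching fall in uncontrolled people.

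*Combined protocol and SAP*

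**What the plan says.** The main objective (Section 2) is "to reduce the gaps in hypertension care and control at population level". Table 1 (Section 1.2) defines the control gap with numerator "Number of aware hypertensives with uncontrolled hypertension + Number of unaware hypertensives" and denominator "The total hypertensive population (aware + unaware"). The only other version is marked "Also calculated in subgroup aware hypertensives". By contrast, Table 1 calculates the diagnosis gap both over everyone surveyed and over hypertensives.

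Section 4.1.4 defines a hypertensive person for the survey as "self-report of previously diagnosed hypertension or without previous diagnosis but presenting an average blood pressure (BP) measurement higher than 140/90 mmHg". A controlled person is one with "self-report of previously diagnosed hypertension and an average BP less than 140/90 mm Hg for patients between 35 and 59 years old or diabetics", with a higher systolic limit of 150 from age 60. Being controlled requires neither treatment nor an earlier raised reading.

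Section 4.2.1 adds BP checks for attenders at health facilities (A.1) and community screening "for all adults without BP readings in the previous year" (C.2), both in the intervention commune. Section 4.2 leaves the control commune on standard care. Section 4.3.1 measures the effect as a difference-in-differences of the gaps.

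**The concern.** BP varies from day to day. Some people whom serial measurement would confirm as hypertensive will read below 140/90 on the survey day. Without a diagnosis they are outside the control-gap denominator. With one, and the same survey reading, they are inside it as controlled. The gap then falls although the number of uncontrolled people has not.

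The added case-finding runs in one commune only, so the shift survives the difference-in-differences and favours the intervention. The adjusted logistic models in Section 4.3.1 cannot be relied on to remove it, because the intervention itself changes who enters the denominator. At stake is whether a fall in the main outcome can be read as better control in the population.

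**Working it through.** **Inputs from the plan.** Section 4.1.2: control gap 45%, difference 10 points, power 0.75, alpha 0.10, 280 hypertensives, prevalence 40%, about 700 people per commune, raised to 1,150 for non-response of 10% and a design effect of 1.5. Section 1.2 (2016 survey): prevalence 43.4%, 36.7% of hypertensives unaware, 41% of the aware uncontrolled.

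**Assumed input.** The share *f* of non-hypertensives who gain a diagnosis and read below threshold at endline irrespective of it. The documents do not give this, so a range is shown.

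**Step 1: the plan's own figure.** Two proportions, 45% against 35%, two-sided alpha 0.10 (sidedness is not stated), power 0.75:

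n = [1.645 × √(2 × 0.40 × 0.60) + 0.674 × √(0.45 × 0.55 + 0.35 × 0.65)]² / 0.10² = 258, or 278 with continuity correction.

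This matches the stated 280 to within 3%, and 280 / 0.40 = 700 as stated. The 10-point target therefore belongs to a 45% gap.

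**Step 2: what one diagnosis does** (survey BP unchanged).
- Raised survey BP, under 60 or diabetic: the person moves from unaware to aware uncontrolled. Numerator and denominator are unchanged.
- Survey BP below 140/90: the person moves from outside the count to aware and controlled. Numerator +0, denominator +1.
- Aged 60 or over, not diabetic, for example 145/85: the person moves from unaware (in the gap) to controlled (out of it). Numerator −1, denominator unchanged.

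The second line is the present point. The third matters for the fix.

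**Step 3: size on the plan's figures.** H = 280 hypertensives, U = 0.45 × 280 = 126 in the gap, 700 − 280 = 420 non-hypertensives, m = *f* × 420, gap = U / (H + m).

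| *f* | m | Gap | Fall (points) | U / 700 |
|---|---|---|---|---|
| 0 | 0 | 126/280 = 45.0% | – | 18.0% |
| 2% | 8.4 | 126/288.4 = 43.7% | 1.3 | 18.0% |
| 5% | 21 | 126/301 = 41.9% | 3.1 | 18.0% |
| 10% | 42 | 126/322 = 39.1% | 5.9 | 18.0% |
| 19% | 80 | 126/360 = 35.0% | 10.0 | 18.0% |

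The last row solves 126 / (280 + m) = 0.35, so m = 80 and 80/420 = 19%. Apparent prevalence would rise from 40% to 360/700 = 51%.

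**Step 4: sensitivity to the starting gap.** The 2016 figures imply a Table 1 gap of 0.367 + 0.633 × 0.41 = 62.7%. With 1,150 × 0.90 = 1,035 respondents there are 449.2 hypertensives, 281.4 of them in the gap, and 585.8 others. At *f* = 2%, 5% and 10% the gap becomes 61.1%, 58.8% and 55.4%, falls of 1.6, 3.8 and 7.2 points. The share of all surveyed stays at 281.4/1,035 = 27.2%.

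**Step 5: the aware-only version.** Same source: 284.3 aware, 116.6 of them uncontrolled, 41.0%. At *f* = 5% it is 116.6 / (284.3 + 29.3) = 37.2%. At 10% it is 116.6 / (284.3 + 58.6) = 34.0%. It is open to the same effect.

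**The case against.** **Safeguards on diagnosis.** Section 4.2.1 (A.2) plans serial and self-measured BP to exclude white coat hypertension, and the screening is aimed at people without a reading in the past year. Both limit the labelling rate. Neither stops a correctly confirmed case from reading below 140/90 on the survey day.

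**Treatment.** Section 1.2 reports that 93% of aware hypertensives were prescribed drugs and 7% of those took none, so about 0.93 × 0.93 = 86% take medication. A reader might infer that every newly diagnosed person found controlled is an artefact. The documents do not support that. Someone who would have read above 140/90 untreated was already in the denominator as unaware, so that person's move to controlled is real. In people whose BP fluctuates around 140/90, treatment also lowers the chance of a raised survey reading. An unchanged numerator is therefore a limiting case.

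**Better ascertainment.** Counting a confirmed hypertensive partly corrects the survey's under-count. That is fair, but the correction is stepped up in one commune and not the other, so it still enters the contrast.

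**Planned outputs.** A reader might infer that the plan leaves no way to see the effect. That goes too far. The diagnosis gap over everyone surveyed, divided by the diagnosis gap over hypertensives, is the prevalence, and control gap × prevalence gives the population share (0.627 × 0.434 = 0.272). What is missing is a stated outcome with its own difference-in-differences, confidence interval and interpretation. The derived figure would also keep Table 1's numerator, with the age-60 problem in Step 2. The facility control indicators in Table 3 do not fill this need, because their denominators are patients enrolled in the cardiovascular risk programme.

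**Conclusion.** The mechanism follows from Table 1 read with Section 4.1.4, and nothing in the plan neutralises it. Case-finding added in one commune can lower the control gap and its aware-only version without a matching fall in uncontrolled people, and that part stays in the difference-in-differences.

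Its size is unknown. At 2% to 10% labelling it is about 1.3 to 5.9 points on the plan's 45% gap, and somewhat more from the higher gap implied by the 2016 survey. These figures assume that no BP changes, that the control commune has no such added labelling, and that *f* lies in the range shown.

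A reader might infer that relabelling alone could produce the planned 10-point effect. On the plan's figures that needs about 19% of non-hypertensives to be labelled, and nothing in the documents suggests such a rate. This is a bias to measure and report. It is not grounds to dismiss a favourable result.

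**What to change.** In Table 1, under Control, add a supplementary outcome:
- **Denominator:** everyone surveyed.
- **Numerator:** survey BP above one cut-off applied to everyone, whether diagnosed or not.

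Changing only the denominator is not enough. Section 4.1.4 classes unaware people and diagnosed non-diabetics aged 60 or over by different thresholds, so a diagnosis can still move the numerator at the same BP. Those thresholds must be reconciled for the outcome.

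Estimate the difference-in-differences of this outcome from both surveys, adjusted for age and sex and allowing for clustering, with its confidence interval. Report by commune the change in the number of diagnosed people with normal survey BP. State in Section 4.3.1 that these results are used to interpret the control gap and are not a pass/fail condition.

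The cost is one more analysis of data that both surveys collect, and a possibly less favourable claim. Precision relative to the effect is lower, which is why it should not be a gate. On the 2016 figures, with 1,035 respondents per survey, a design effect of 1.5 and Table 1's numerator as a stand-in:
- **Control gap:** a 10-point fall has standard error √(4 × 1.5 × 0.627 × 0.373 / 449) = 5.6 points, z about 1.8.
- **Share of all surveyed:** the same change is 0.434 × 10 = 4.3 points, with standard error √(4 × 1.5 × 0.272 × 0.728 / 1,035) = 3.4 points, z about 1.3.
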